- m Patients should not take BI 891065 prior to certain visits that require pre-dose blood sampling as detailed in [Table 10.3: 4](#). Patients could be assigned q.d. or b.i.d. dosing. For patients taking b.i.d. dosing, the evening dose on infusion days should be skipped (Day 1 and Day 15 of Cycle 1). For all patients, the morning dose on Day 2 and Day 16 should be taken in the clinic (after pre-dose blood sampling is taken). On BI 754091 infusion days, BI 891065 will be administered approximately 30 minutes after the end of the BI 754091 infusion.. Patients will be observed after their first dose of BI 891065 on Cycle 1 Day 1 and Cycle 2 Day 2 for 4 hours as outlined in Section [5.2.6.4.3](#).
- n An EOT visit should be performed for all patients who permanently discontinue trial medication. If the decision to permanently discontinue treatment is taken at a scheduled visit, the EOT visit should be performed instead of the scheduled visit (preferably within 7 days and no later than 14 days after the last treatment). Please note that a patient with an initial radiologic PD does not have to be automatically withdrawn from treatment (see Section [3.3.4.1](#)).
- o The residual effect period starts after last dose of trial medication and ends 30 days later. A 30-day safety FU visit should take place before any other anti-cancer treatment starts.
- p Follow-up for PD visits for tumour assessment by imaging (CT or MRI) for patients who discontinue trial treatment without having PD based on RECIST v1.1 and/or iRECIST should be performed every 6 weeks (±5 days) for the first 6 months of treatment and then every 9 weeks (±5 days) thereafter until PD or another withdrawal criterion is met. At these visits, serious adverse events (SAEs) and adverse events of special interest (AESIs) occurring during the trial that are considered to be related to trial treatment or procedures will be followed until resolution.

TABLE OF CONTENTS

[figure not shown]
TITLE PAGE	1
CLINICAL TRIAL PROTOCOL SYNOPSIS	2
FLOW CHART: BI 1379.1 (REFMAL 505) PART A TRIAL ASSESSMENTS	6
FLOW CHART: BI 1379.1 (REFMAL 505) PART B TRIAL ASSESSMENTS	10
FLOW CHART: BI 1379.1 (REFMAL 505) PART C (NSCLC) TRIAL ASSESSMENTS	15
TABLE OF CONTENTS	19
ABBREVIATIONS	24
1. INTRODUCTION	26
1.1 MEDICAL BACKGROUND	26
1.2 DRUG PROFILES	27
1.2.1 BI 891065 [REDACTED]	27
1.2.2 BI 754091 [REDACTED]	28
1.2.3 Combination of BI 891065 and BI 754091	28
1.3 RATIONALE FOR PERFORMING THE TRIAL	29

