- c Safety laboratory assessments including haematology, serum biochemistry, coagulation, serum pregnancy test, and urinalysis will be performed locally. The following screening parameters should be done ≤ 14 days prior to initiation of treatment: medical history and demographics, physical examination (including height and weight), Eastern Cooperative Oncology Group (ECOG) performance status, vital signs, electrocardiogram (ECG), haematology (per Section 5.2.3), clinical chemistry (sodium, potassium, phosphate, chloride, creatinine, calcium, venous bicarbonate HCO_3 , albumin, total protein, aspartate aminotransferase [AST], alanine aminotransferase [ALT], alkaline phosphatase, total, direct and indirect bilirubin, lactate dehydrogenase, serum glucose, creatinine kinase [CK: if CK is elevated, then CK-MB, Troponin I, and myoglobin should be reactively tested, with further follow-up as clinically warranted], serum urea nitrogen, and serum uric acid), urinalysis, and screening pregnancy test. If these assessments are performed within 72 hours of initiation of treatment, they do not need to be repeated on Cycle 1 Day 1 with the exception of the ECOG performance status, an abbreviated physical examination, vital signs, and single/triplicate ECGs required as outlined in Section 5.2.4 and Table 10.3: 1. Tumour assessments (scans) should be performed ≤ 28 days prior to initiation of treatment. Refer to Section 5.2.3 for additional details. Vital signs (blood pressure, body temperature, and pulse rate) are checked at every visit prior to blood work and trial treatment and at the discretion of the Investigator (see Section 5.2.2).
- d Physical examinations including the measurements of height (screening only) and weight will be done at screening, on Day 1 of each treatment cycle, at the end-of-treatment (EOT) visit, at the 30-day safety follow-up (FU) visit, and at the FU visits for PD. However, patients will have an additional abbreviated physical examination (focused on the specific disease, at the Investigator's discretion) on Cycle 1 Day 15. ECOG performance status will be done at screening, on Day 1 of Cycles 1 and 2, on Day 1 of every other cycle beginning with Cycle 3, at the EOT visit, at the 30-day FU visit, and at FU visits for PD (see Section 5.2.1).

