Treatment day	Up to 28 days ^b	1	2	8	12	15	16	17	1 (±2)	1 (±2)		+1 week	±5 days
Informed consent	X												
Inclusion / exclusion criteria	X	X											
Medical history and demographics ^c	X												
Report planned hospitalisations	X												
Physical examination, height (screening only), and weight ^{c,d}	X	X				X			X	X	X	X	X
Vital signs ^{c,e}	X	X	X	X	X	X	X	X	X	X	X	X	X
ECOG Performance score ^{c,d}	X	X							X	X	X	X	X
Electrocardiograms (single/triplicate) ^{c,e}	X	X	X			X	X		X	X	X		
Cardiac testing (only if cardiac disease suspected) ^f	X												
Serum pregnancy test ^{c,g}	X	X							X	X	X	X	
Safety laboratory (haematology, biochemistry) ^c	X	X			X	X			X	X	X		
Safety laboratory (amylase and lipase if symptoms of pancreatitis)		X							X	X	X		
Safety laboratory (coagulation) ^c	X	X							X	X	X		
Alpha-1 acid glycoprotein (AGP)		X							X				
Virology testing (≤28 days of treatment)	X												
Safety laboratory (urine) ^c	X	X			X	X			X	X	X		
Tumour assessment ^{c,h}	X	Every 6 weeks (then every 9 weeks after 6 months of treatment)									X		X
Blood sampling for BI 891065 pharmacokinetics ⁱ		X	X	X	X	X ^j	X ^j	X ^j	X				
Blood sampling for BI 754091 pharmacokinetics ⁱ		X	X	X	X	X	X	X	X	X	X	X	
Food administration for Food Interaction Assessment ⁱ							X						

Proprietary confidential information © 2020 Boehringer Ingelheim International GmbH or one or more of its affiliated companies

Part B Flow Chart Trial period	Screening	Part B Dose Escalation BI 891065 + BI 754091 Combination Treatment Period									EOT ^p	30-day Safety FU ^q	FU for PD ^r
		C1							C2	C3+			
Cycle ^a													Every 6 or 9 weeks
Visit number	1	2	3	4	5	6	7	8	9	10+			
Treatment day	Up to 28 days ^b	1	2	8	12	15	16	17	1 (±2)	1 (±2)		+1 week	±5 days
Tumour biopsy (cIAP degradation) ^m	X								X				
BI 891065 intake ⁿ		X	X	X	X	X	X	X	X	X			
BI 754091 administration ⁿ		X							X	X			
Concomitant therapy	X	X	X	X	X	X	X	X	X	X	X	X	X
Adverse events	X	X	X	X	X	X	X	X	X	X	X	X	
Dose-limiting toxicity (DLT) assessment ^o		X	X	X	X	X	X	X	X	X	X		
SAEs/AESIs considered drug-related													X
Patient status												X	X
Review Patient Diary	X	X	X	X	X	X	X	X	X	X	X		

Part B Dose Escalation BI 891065 + BI 754091 Flow Chart Footnotes

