- a Treatment cycles (C) are 21 days (3 weeks). Patients may continue treatment with BI 891065 and BI 754091 as long as they are deriving benefit according to the Investigator's judgment. All circumstances for withdrawal of trial treatment are presented in Section 3.3.4.1.
- b Screening should take place within 28 days of start of study treatment, however, may be extended as outlined in Section 6.2.1.1.
- c Safety laboratory assessments including haematology, serum biochemistry, coagulation, serum pregnancy test, and urinalysis will be performed locally. The following screening parameters should be done ≤ 14 days prior to initiation of treatment: medical history and demographics, physical examination (including height and weight), Eastern Cooperative Oncology Group (ECOG) performance status, vital signs, electrocardiogram (ECG), haematology (per Section 5.2.3), clinical chemistry (sodium, potassium, phosphate, chloride, creatinine, calcium, venous bicarbonate HCO_3 , albumin, total protein, aspartate aminotransferase [AST], alanine aminotransferase [ALT], alkaline phosphatase, total, direct and indirect bilirubin, lactate dehydrogenase, serum glucose, creatinine kinase [CK: if CK is elevated, then CK-MB, Troponin I/Troponin T, and myoglobin should be reactively tested, with further follow-up as clinically warranted], serum urea nitrogen, serum uric acid, and thyroid panel [TSH, free T4, and free T3]), urinalysis, and screening pregnancy test. If these assessments are performed within 72 hours of initiation of treatment, they do not need to be repeated on Cycle 1 Day 1 with the exception of the ECOG performance status, an abbreviated physical examination, vital signs, and single/triplicate ECGs as outlined in Section 5.2.4 and Table 10.3: 2 required prior to first administrations of trial treatments. Tumour assessments (scans) should be performed ≤ 28 days prior to initiation of treatment. Refer to Section 5.2.3 for additional details. Vital signs (blood pressure, body temperature, and pulse rate) are checked at every visit prior to blood work and trial treatment and at the discretion of the Investigator (see Section 5.2.2).

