4.1.7 Dose reductions and dose delays

AEs that are immune related should be managed according to the Guidelines for irAE management (as outlined in Appendix 10.2).

For Grade 4 AE/SAEs that are not immune related, study drug should be withdrawn. However, if it can be excluded with high certainty that the event was related to study medication, study drug should be paused, and resumption of study drug may be allowed after discussion with the Medical Monitor and the Sponsor.

For Grade 3 AE/SAEs that are not immune related, study drug should be paused.

For Grade 2 AEs/SAEs that are not immune related but are deemed intolerable by the patient or the treating physician and not responding to appropriate medical management, the physician should decide if a pause of treatment is warranted considering relevant variables such as perceived relatedness to study drug.

[figure not shown]
If, after a treatment pause of ≤ 12 weeks, the non-immune related SAE/AE resolves to baseline or Grade 1 and the physician thinks it is clinically appropriate to restart study drug, then the physician may choose to restart BI 891065 at one dose lower than the dose administered before the pause, and BI 754091 at the same fixed dose of BI 754091. If the AE/SAE prompting interruption has unequivocally been excluded to be drug related, reintroduction of BI 891065 at the same dose as prior to the pause may be considered.

There will be no dose reductions or escalations of BI 754091 in any one patient. However, in the event of an infusion-related reaction \leq Grade 2, the infusion rate of BI 754091 may be decreased by 50% or interrupted until resolution of the event and re-initiated at 50% of the initial rate until completion of the infusion. In patients experiencing infusion-related reactions \leq Grade 2, subsequent infusions may be administered at 50% of the initial rate. If an infusion-related reaction is Grade 3 or higher in severity at any point during the study, treatment with BI 891065 and BI 754091 will be permanently discontinued (see Section 5.2.6.4.2).

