4.1.8 Definition of dose-limiting toxicity

Dose-limiting toxicities (DLTs) will be recorded throughout the trial. Any DLT must be reported to the [REDACTED] Medical Monitor by the Investigator or designee within 24 hours of first knowledge, and to the [REDACTED] as an SAE when appropriate. All DLTs will be agreed upon between the Sponsor, the Study Chair, the [REDACTED] Medical Monitor, and the Investigators after review of the data from each cohort. Only DLTs starting in the first cycle of monotherapy during Part A or during the first cycle of BI 891065 in combination with BI 754091 during Part B are necessary for dose-escalation decisions made by the SRC. DLT information from later cycles will be taken into consideration if available.

All relevant safety information (including DLTs) together with data on target engagement will be considered when selecting the recommended doses for the expansion cohorts.

Severity of AEs will be graded according to CTCAE Version 5.0. Any of the following AEs will be classified as DLTs following review by the Investigators and the [REDACTED] Medical Monitor unless unequivocally due to underlying malignancy or an extraneous cause.

Haematologic toxicities:

- For patients with solid tumours:
 - Any Grade 5 toxicity
 - Neutropenia \geq Grade 4 lasting for >5 days
 - Febrile neutropenia of any duration (ANC $<1.0 \times 10^9$ cells/L and fever $\geq 38.5^\circ\text{C}$)
 - Neutropenia Grade 3 with documented infection
 - Grade 4 thrombocytopenia, or Grade 3 thrombocytopenia with bleeding or a requirement for platelet transfusions
 - Grade 4 anaemia unexplained by underlying disease.

Non-haematological toxicities:

- AST or ALT >3 times ULN and concurrent total bilirubin >2 times ULN without initial findings of cholestasis (e.g., findings consistent with Hy's law or the FDA definition of potential DILI)
- \geq Grade 4 AST or ALT of any duration
- Any \geq Grade 3 non-haematologic toxicity with the following exceptions:
 - Grade 3 irAE that resolves to \leq Grade 1 or to baseline with immunosuppressive therapy within 2 weeks
 - Grade 3 fatigue that persists <7 days
 - Grade 3 rash that resolves to \leq Grade 1 within 2 weeks
 - Grade 3 or 4 elevation in serum amylase and/or lipase that is not associated with clinical or radiographic evidence of pancreatitis
 - Grade 3 electrolyte abnormality that lasts <72 hours, is not clinically complicated, and resolves spontaneously or responds to conventional medical intervention

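### Part B schedules no haematology or biochemistry on Cycle 1 Day 8, so a short, silent laboratory DLT in the first week can go unseen

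*Protocol*

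**What the plan says.** Protocol section 5.2.3 leaves the timing of safety laboratory tests to the flow charts. The row beginning "Safety laboratory (haematology, biochemistry" appears in both escalation charts:

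- **Part A, Cycle 1:** Days 1, 8, 12 and 15.
- **Part B, Cycle 1:** Days 1, 12 and 15. The Day 8 cell is empty.

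Both parts have the next panel on Cycle 2 Day 1 (±2 days). Day 8 is a visit in Part B: the row "Blood sampling for BI 891065 pharmacokinetics" is marked, as are BI 754091 blood, vital signs, adverse events and DLT assessment. No footnote adds a Day 8 panel. Footnote c in both charts allows the Day 1 panel to be skipped: "If these assessments are performed within 72 hours of initiation of treatment, they do not need to be repeated on Cycle 1 Day 1".

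Section 4.1.8 includes laboratory DLTs with no minimum duration, for example "Grade 4 thrombocytopenia, or Grade 3 thrombocytopenia with bleeding or a requirement for platelet transfusions" (its Grade 4 limb) and "AST or ALT >3 times ULN and concurrent total bilirubin >2 times ULN". SAP section 6.1 sets the MTD evaluation period at 21 days from the start of Cycle 1 for all patients.

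**The concern.** For the combination, the first scheduled on-treatment panel is on Day 12; for monotherapy it is on Day 8. The Day 8 DLT review in Part B therefore has no scheduled laboratory result from after the first dose.

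Two things follow. A laboratory DLT that starts in the first week without symptoms and clears before Day 12 can go unseen, and the patient then enters the dose-toxicity model as DLT-free. An abnormality that lasts is still found and counted in Cycle 1, but the patient may take BI 891065 for up to 4 more days before a value is known that section 4.1.7 answers with a pause: "For Grade 3 AE/SAEs that are not immune related, study drug should be paused".

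Single DLTs can matter to the model. In the protocol's hypothetical scenarios (Table 10.5: 11), no DLT in 4 patients at 200/240 mg opens 400/240 mg, while 1 DLT in 3 does not. Those scenarios use an earlier prior and do not show that any decision was affected.

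**Working it through.** The plan gives no figure on this point, so there is none to reproduce.

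**Reading of the charts.** The Part B columns are aligned as extracted. The only physical examination mark between Cycle 1 Day 1 and Cycle 2 falls on Day 15, as footnote d requires. The Cycle 1 ECG marks fall on Days 1, 2, 15 and 16, as in Table 10.3: 2.

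**Gaps.** Day 1 to the next panel is 12 − 1 = 11 days in Part B and 8 − 1 = 7 days in Part A. If the 72-hour waiver is used, these become 14 and 10 days; the extra 3 days lie before dosing and are equal in both parts.

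**Chance that a scheduled sample falls within the event.** Samples after Day 1 are A = {8, 12, 15, 22} and B = {12, 15, 22}. An event with onset t and duration d is caught by a sample on day s if t ≤ s < t + d. Assumptions, not from the documents: uniform onset, fixed duration, no symptom-driven test.

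For onset on Days 1-8 (7 days wide):

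- Part A: min(7, d)/7
- Part B: min(7, max(0, d − 4))/7

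| Duration d | Part A | Part B |
|---|---|---|
| 3 days | 3/7 = 43% | 0/7 = 0% |
| 4 days | 4/7 = 57% | 0/7 = 0% |
| 7 days | 7/7 = 100% | 3/7 = 43% |
| 10 days | 7/7 = 100% | 6/7 = 86% |
| 11 days | 7/7 = 100% | 7/7 = 100% |

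The Part B zero for events shorter than 4 days holds for any onset pattern within Days 1-8.

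Averaged over onset on Days 1-22, for the three possible days of the last draw:

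| Last draw | d = 3, A vs B | d = 7, A vs B |
|---|---|---|
| Day 20 | 12/21 vs 9/21 (57% vs 43%) | 19/21 vs 15/21 (90% vs 71%) |
| Day 22 | 12/21 vs 9/21 (57% vs 43%) | 21/21 vs 17/21 (100% vs 81%) |
| Day 24 | 10/21 vs 7/21 (48% vs 33%) | 19/21 vs 15/21 (90% vs 71%) |

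The difference is [min(7, d) + min(4, d) − min(11, d)]/21, whatever the last draw: 3/21 = 14 points for 3 days, 4/21 = 19 points for 4 to 7 days, 1/21 = 5 points for 10 days, and 0 from 11 days.

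**Lasting events.** The first sample comes 12 − 8 = 4 days later for onset on Days 1-8 and 0 days later for onset after Day 8. Averaged over the cycle this is 4 × 7/21 = 1.33 days.

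**Patients still to be reached.** Table 7.1.2: 5 shows 6 + 8 + 5 = 19 evaluable Part B patients by 13 November 2019. Section 7.7 expects about 31-37, leaving at most 31 − 19 = 12 to 37 − 19 = 18. These are upper bounds, because non-evaluable patients are not counted.

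**The case against.** The strongest reply is that the blank is deliberate. Cycle 1 panels step down from four in Part A to three in Part B and one in Part C, and post-dose surveillance steps down too (10 hours, then 8 and 6, then 4). DLT review is marked at all seven Part B Cycle 1 visits but panels at only three, so the plan does not tie review to a same-day panel. This makes intent plausible, but no rationale is written. Part C is also a weak comparator: its primary endpoint is response, whereas Part B estimates DLTs and the MTD.

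The second reply is that the missed event is narrow. It must start on Days 1-8, stay silent, and fall below the criterion before Day 12 while dosing continues. That stands. A Grade 4 AST or ALT rise that is still Grade 3 on Day 12 would normally still count under the rule on "Grade 3 non-haematologic toxicity with the following exceptions". Part A had no DLT in 22 evaluable patients and BI 754091 alone none in 77 (Tables 7.1.2: 2 and 7.1.2: 4). These data do not exclude toxicity of the combination. The Amendment 5 log also says that haptoglobin and reticulocytes were added because of isolated bilirubin increases, without giving the trial part or timing.

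Third, the percentages rest on assumed onset and duration. That also stands: they are illustrative, and the first table covers the only window in which the schedules differ. Part A itself misses 57% of 3-day events with onset on Days 1-8.

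Fourth, adding the panel late makes detection differ between cohorts in one model, and the later cohorts may be on b.i.d. dosing. This is a real drawback and should be disclosed.

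**Conclusion.** The point holds as a worthwhile, inexpensive improvement. Two results depend on the schedule alone: a lasting abnormality with onset on Days 1-8 is first sampled 4 days later in Part B than under the Part A schedule, and a silent event with that onset that clears before Day 12 cannot meet a scheduled Part B sample. The detection percentages also need uniform onset, fixed duration and no symptom-driven test. Over the whole cycle the loss is 14 points for 3-day events and 19 points for 7-day events, among events whose frequency is unknown. The number of DLTs missed, and any effect on dose decisions, cannot be estimated from the documents. The point concerns scheduled samples only; investigators may always test on symptoms.

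**What to change.** Mark haematology and biochemistry on Cycle 1 Day 8 in the Part B flow chart for all further Part B patients, using the existing visit and blood draw. In the clinical trial report, next to the Part B DLT table, state that earlier cohorts had no scheduled Day 8 panel. If Part B enrolment is already complete, only that sentence applies.

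The cost is one flow chart cell, one local panel per further patient (at most about 12-18 patients from the November 2019 count) with no extra visit or needle stick, and one sentence in the report. The drawback is slightly different laboratory DLT detection between earlier and later cohorts in the same model, which the sentence discloses.

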1. INTRODUCTION

[figure not shown]
1.1 MEDICAL BACKGROUND

Despite the recent advancements in cancer treatment, cancer remains a leading cause of death globally. In the United States (US), approximately 1,685,210 new cancer cases were expected to be diagnosed in 2016. The American Cancer Society estimated that there would be approximately 595,000 deaths due to cancer in the US during 2016 (R16-4925). The type of cancer chosen for the expansion cohort in this trial is non-small-cell lung cancer (NSCLC).

Non small-cell lung cancer

[figure not shown]
Lung cancer remains the most common cancer in the world. In the US, the American Cancer Society estimated that approximately 224,390 new cases of lung cancer and 158,080 deaths from lung cancer were expected in 2016 (P16-11525). The most prevalent (80% to 85%) of all lung cancers is NSCLC. At initial diagnosis, 55% of patients have distant spread of disease (R16-4724). According to the US National Cancer Institute (NIH), the 5-year relative survival of distant stage disease is 4.9% (R16-4740). Real-world data (FRAME study [R16-3671]), has shown median overall survival (OS) in patients with advanced or metastatic NSCLC of 10.3 months. This is in the range (7.4 to 11.8 months) obtained from Phase III studies (R04-1314; R08-4164; R12-3987; R07-4508).

Treatment of advanced stage NSCLC is changing at the moment. Pembrolizumab was approved that year by the Food and Drug Administration (FDA) for 1st-line treatment of patients with metastatic NSCLC with high levels of programmed cell death protein ligand 1 (PD-L1) (tumour proportion score $\geq 50\%$) (R16-5013). First-line treatment of patients with advanced NSCLC who are not pembrolizumab candidates consists of 4 to 6 cycles of platinum-based chemotherapy. The 2nd line treatment of NSCLC has also been markedly transformed by the introduction of PD-1/PD-L1 immune checkpoint inhibitor monoclonal antibodies (mAbs) (nivolumab, durvalumab and atezolizumab in addition to pembrolizumab). Treatment of patients with advanced NSCLC with nivolumab, pembrolizumab, or atezolizumab monotherapy results in very durable responses in approximately 15% to 20% of patients (R15-3715; R15-6023; R16-0876).

[figure not shown]
1.2 DRUG PROFILES

1.2.1 BI 891065

[figure not shown]

1.2.2 BI 754091

1.2.3 Combination of BI 891065 and BI 754091

The rationale for combining BI 891065 and anti-PD-1 is the “one two punch” combination

[REDACTED]

For a more detailed description of BI 891065 and BI 754091, profiles please refer to the current Investigator's Brochures.

